8.6 DATA MANAGEMENT

The CROs in charge of the study is

The data entered into the eCRFs by investigational staff will be reviewed for completeness and accuracy and the site personnel will be instructed to data entry data into the eCRFs and to make any required corrections or additions during the phone training. The eCRF will be provided by online edit checks. The Data Manager will perform the cleaning session by running post-entry checks by means of validation programs and data listings specific for the study. During this process, if clarifications are needed, the Data Manager will raise queries by means of data query forms through the application. Designated investigator site staff is required to respond to the query and make the correction to the database.

Patients violating inclusion or exclusion criteria will not be considered for analyses. A description of reasons of violation will be provided anyway. After these actions have been completed and the database has been declared to be completed and accurate, it will be locked and made available for data analysis. Any changes to the database after that time can only be made by joint written agreement between the Medical Adviser, the Study Statistician and the Data Manager. Only authorized and well-documented updates to the study data will be possible after database lock.

Each participating site will maintain appropriate medical and research records for this study, in compliance with GPP and regulatory and institutional requirements for the protection of confidentiality of subjects.

Patient initials or names will not be recorded in the database: patients will be associated to a unique identifier, assigned as a progressive number within each site. Due to the observational nature of the study no independent review of the data will be performed.

Data access rules, as well as data transfer to Sponsor, will be detailed in the Data Management Plan.

8.7 DATA ANALYSIS

The statistical analysis will be performed on all evaluable patients who enter the study and meet the inclusion criteria. Patients with missing values will not be excluded from the analysis, their data will not be replaced; frequency of missing data will be given for all analyzed variables.

Descriptive analysis will be composed of means, medians, quantiles, proportions (with their respective 95% confidence intervals, CI) and contingency tables according to the nature of the variables. As a dispersion measurement the standard deviation and the interquartile range will be calculated. All events during follow-up will be described as incidence rates with 95% CI.

Statistical analysis will be performed using the SAS software.

The study objectives will be evaluated as follows:

Primary objective

To describe the clinical course of IPF during 12 months of observation

At each follow up visit the frequency of IPF symptoms (cough, fatigue, dizziness, chest pain, clubbing, bibasilar crackles) will be provided and the variation between visits will be described too mostly in terms of incident and worsening symptoms. Moreover, the score of the Modified Medical Research Council Dyspnea Scale for the evaluation of dyspnea at each follow up visit will be calculated together with the variation since baseline and between follow up visits.

The following outcomes will be also considered during the 12-month observation: lung function parameters (like VC, FVC, FEV1, TLC, DLCO, pO₂, pCO₂; SaO₂, PaO₂ and PaCO₂ at rest) and patient's exercise capacity (evaluated by means of 6-minute walked distance test, if available). The outcomes will be described at each follow up by means of descriptive statistics and the variation between visits will be provided too.

Secondary objectives

#1 Description of IPF patients at enrollment (socio-demographic data, IPF risk factors, comorbidities, disease severity and manifestation, methods for diagnosis, treatment modalities)

IPF patients enrolled at baseline will be described in terms of socio-demographic variables (e.g. age, gender, race, body mass index, educational degree, and employment status) and potential IPF risk factors (such as smoking habits, environmental exposure, drug exposure, other factors).

The absolute and relative frequency distributions of patients (N, %) according to ongoing comorbidities (such as gastroesophageal reflux disease, pulmonary hypertension, emphysema, lung cancer, coronary heart disease, depression) will be also provided at baseline.

Treatment modalities will be described at each visit by means of frequency distribution of patients according to ongoing therapies for IPF; pharmacological (such as steroids, anticoagulants, immunomodulators, N-acetylcysteine, pirfenidone, etc..) and non-pharmacological (such as long term oxygen and pulmonary rehabilitation) therapies will be considered and described in terms of drug, dosage regimen and duration/number of sessions (including start and stop dates). The frequency of patients on listing for lung transplantation at baseline will be also provided.

#2 To describe the frequency of exacerbations during 12 months of observation

The proportion of patients with at least one exacerbation after 12 months of observation will be computed as the ratio between the number of patients with one or more episodes of

exacerbation occurred during 12 months of follow up over the total number of evaluable patients. Patients who drop-out without having exacerbations before the end of the study, will be considered in the denominator of the proportion of interest. The median number of episodes of exacerbation per patient will be provided. Finally time to first exacerbation will be analyzed by Kaplan-Meier curves.

#3 To describe the HRQoL variation during 12 months of observation

The digits for EQ-5D-5L 5 dimensions can be combined in a 5-digit number describing the respondent's health state. An appropriate algorithm will be used to summarize data in an overall score ranging from -1 (worse-than-death health status) to 1 (best health status) [38, 48].

The descriptive statistics will be produced for EQ-5D-5L descriptive system index and VAS. Moreover, the difference of scores between baseline and available follow up visits will be calculated too.

Similarly, the descriptive statistics of St. Georges Respiratory Questionnaire scores (symptoms, activity and impacts and total score) will be calculated. The St. Georges Respiratory Questionnaire is a self-completed questionnaire for measuring impaired health in patients with chronic lung disease. The descriptive statistics of weighted single scores (symptoms, activity and impacts and total score) will be calculated. Graphs of mean HRQoL scores according to visits will also be provided to show the trend of variation, if any.

#4 To describe health care sector-related costs during 12 months of observation

In order to describe health care sector-related costs at diagnosis and from diagnosis up to the end of 12-month follow-up according to the INHS point of view, a two steps approach will be followed: (i) first of all the resource consumption since diagnosis will be collected or estimated and then (ii) a monetary value will be assigned to the collected or estimated resource consumption.

(i) Health care resource consumption exclusively related to both IPF and IPF-related adverse events will be computed during observational period in terms of pharmacological and non-pharmacological treatments, number of (inward and day-hospital) hospitalizations, number of emergency room visits, number of General Practitioner visits, laboratory tests or examinations (spirometry, BAL, saturation), number of imaging sessions. Health care resources consumed during a three-month span of time between date of diagnosis and inclusion in the study will be retrospectively collected via an ad hoc section of the case report form (CRF) and/or estimated.

(ii) In order to estimate the economic impact on health care sector-related costs of the above mentioned health services (hospital admissions, visits, treatments, examinations) consumption, a monetary value to each event recorded will be assigned, as defined by the Italian Ministry of Health through the tariff in force for outpatient setting [28]. The cost of hospitalization will be valued according to the most recent available diagnosis-related group (DRG) tariffs; finally pharmacological treatments will be costed at consumer price.

All costs will be expressed in €. A monthly (or yearly) cost will be provided by taking into account patients according to duration of observation and parametrizing each patient to the 1-year observation period.

Cost of Illness (COI) will be analyzed via descriptive statistics (mean; standard deviation; median; minimum and maximum).

Non-parametric bootstrap method will be applied to COI data for calculating 95% confidence intervals.

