6. RATIONALE AND BACKGROUND

Idiopathic pulmonary fibrosis (IPF) is a rare disease of unknown etiology that is characterized by progressive fibrosis of the interstitium of the lung, leading to decreasing lung volume and progressive pulmonary insufficiency [1][2], presenting more frequently in men than in women and is usually diagnosed in people over 50 years of age, particularly those with a history of cigarette smoking [2].

Several potential risk factors for the development of IPF have been identified. These include environmental and occupational exposures, tobacco smoking, comorbidities (in particular gastroesophageal reflux disease [GERD]), and genetic polymorphisms. The identification of risk factors for IPF is critically important as it may inform prevention strategies, early diagnosis, and novel therapies [16].

There is a strong association (prevalence of approximately 90%) between gastroesophageal reflux and IPF [17-20]. Moreover, although a causal relationship is unclear, it has been hypothesized that gastroesophageal reflux may be a risk factor for microaspiration, and this may be important in the pathogenesis and natural history of IPF [21].

IPF also appears to be more common in men compared to women, however, some postulate this may be due to sex differences in historical smoking patterns rather than an inherent sex-related risk for IPF [16].

Idiopathic Pulmonary Fibrosis is usually associated with a poor prognosis: the clinical course of IPF can be unpredictable [3][4]. IPF progression is associated with an estimated median survival time of 2 to 5 years following diagnosis [1][2]. The 5-year survival for IPF ranges between 20% and 40% [4].

Recognizing IPF in clinical practice can be challenging as symptoms often appear similar to those of more common diseases. This contributes to delay the diagnosis which is usually made 6 to 24 months after initial symptoms [7,8]. An earlier diagnosis of IPF is a prerequisite for earlier treatment and, potentially, improvement of the long-term clinical outcome[1]. A multidisciplinary approach involving a pulmonologist, radiologist and pathologist expert in interstitial lung disease has been shown to improve the accuracy of IPF diagnosis[2][5][6].

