Dyspnea and cough are hallmark symptoms of IPF, and both appear to have important effects not only on quality of life (QoL) but also on survival [15]. IPF patients have unpredictable acute exacerbations, which could occur even with mild physiological impairment. At least half of hospitalizations are thought to be due to acute exacerbations of IPF [16]. Acute exacerbations of IPF are defined as an unexplained worsening or development of dyspnea. Their yearly incidence is between 10 and 15% of all patients. The prognosis of exacerbations is poor, with mortality ranging from 78% to 96% [22]. Other causes of exacerbations such as pulmonary embolism, congestive heart failure, pneumothorax, or infection need to be excluded.

Moreover, IPF patients experience depressive symptoms, which are correlated to QoL impairment and fatigue. QoL is further worsened as daily activities become restricted and patients grow increasingly oxygen dependent, debilitated, and dependent on others [15]. Not only prevalence of IPF is higher in men and in the older age groups, but also burden of disease [14]. In fact, higher increase in hospital admissions was found in men and older age groups by Navaratnam and colleagues [14]. They also estimated that the financial burden from IPF inpatient care alone in England is currently £16 million and will be almost £20 million by 2020.

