8.5 STUDY SIZE

The sample size was determined on the basis of feasibility criteria. In fact, according to the volume of patients managed by the centers involved in this study, inclusion of 200 subjects (10 patients/center) with the characteristics defined at Inclusion/Exclusion criteria paragraphs is deemed reasonable for enrolment period (18 months).

An evaluation of the possible achievable precision of the estimates was performed considering the primary objective of the study and literature data, when available.

The primary objective of the study is to describe the clinical course during 12 months of observation, in terms of symptoms, lung function and exercise tolerance. Assuming a drop-out rate ranging from 20% to 40%, the total number of evaluable patients at 12-month follow-up visit is expected to range between 120 and 160 subjects. Drop-out rate was hypothesized by considering mortality rate in IPF patients and natural drop-out from studies. Literature data about the clinical course of outcomes of interest in IPF patients in a real-life context are scanty. Nishiyama et al. [35] conducted a study on 93 IPF patients and assessed the pulmonary function. The mean (\pm SD) of FVC, FEV1, DLCO were 2.37 (\pm 0.73) L, 1.93 (\pm 0.57) L and 9.19 (\pm 3.92) mL*min⁻¹*mmHg⁻¹ respectively. According to the data of a recently completed trial on patients with IPF by Swigris et al [37], the mean (\pm SD) baseline

6-min walked distance was 372.9 (± 82.63) meters. Regarding the most common IPF symptoms, clubbing, dyspnea (evaluated by means of a mMRC score ≥ 2), crackles and cough frequencies are 43%, 44%, 67% and 73% respectively [34, 35].

Table 1 shows the two-sided 95% confidence interval (CI) for expected frequency of IPF symptoms for a sample size n=120 and 160, using the large sample normal approximation [36].

| | Expected frequency | 95% CI | | | |
|--------------------------------|--------------------|--------|-------|--|--|
| IPF symptoms | | | | | |
| n=120 | | | | | |
| Clubbing | 43% | 34.1% | 51.9% | | |
| Dyspnea (mMRC score ≥ 2) | 44% | 35.1% | 52.9% | | |
| Crackles | 67% | 58.6% | 75.4% | | |
| Cough | 73% | 65.1% | 80.9% | | |
| n=160 | | | | | |
| Clubbing | 43% | 35.3% | 50.7% | | |
| Dyspnea (mMRC score ≥ 2) | 44% | 36.3% | 51.7% | | |
| Crackles | 67% | 59.7% | 74.3% | | |
| Cough | 73% | 66.1% | 79.9% | | |

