An exacerbation will be considered occurred during observation period if onset date **[F08_EXACERBATIONS.Ex_Exacer_1_Ons_date-Ex_Exacer_10_Ons_date]** >=date of first IPF diagnosis (mm/yyyy) **[F05_DIAGNOSIS_IPF.DIA_Date_IPF_diagnosis]** and onset date **[F08_EXACERBATIONS.Ex_Exacer_1_Ons_date-Ex_Exacer_10_Ons_date]** <= last available visit date **[P16_PATIENT_DISPOSITION.PD_2]** (for patients who completed the study **[F19_STUDY_COMPLETION.SC_1]** = Yes) OR date of Date of drop out or death **[F19_STUDY_COMPLETION.SC_4, SC_5]** (for patients who did not complete the study **[F19_STUDY_COMPLETION.SC_1]** = No).

Health Related Quality of Life (HRQoL) EQ-5D-5L (see Appendix 8.3)

The EQ-5D-5L is a standardized measure of health status, it is filled in by patients. It consists of 2 sections: "EQ-5D descriptive system" and EQ visual analogue scale (EQ VAS).

²Perez T. et al. Modified Medical Research Council scale vs Baseline Dyspnea Index to evaluate dyspnea in chronic obstructive pulmonary disease *Int J Chron Obstruct Pulmon Dis.* 2015; 10: 1663-1672.

The EQ-5D-5L descriptive system comprises the following 5 dimensions: mobility, self-care, usual activities, pain/discomfort and anxiety/depression.

The EQ VAS indicate the health status self-assessed by the patient on a visual analogue scale from 0 to 100, where 100 is the "best imaginable health state" and 0 the "worst imaginable health state". It can be used as a quantitative measure of health as judged by respondents.

St. George's Respiratory Questionnaire (SGRQ) (see Appendix 8.5)

The SGRQ is designed to measure health impairment in patients with asthma and COPD.

There is a report of its validation in a small study of adults with cystic fibrosis (Archivos de Bronconeumologia Volume 43, Issue 4, April 2007, pages 205-211). It is in two parts. Part 1 produces the Symptoms score, and Part 2 the Activity and Impacts scores. A Total score is also produced.

Part 1 (Questions 1-8) addresses the frequency of respiratory symptoms. It is not designed to be a precise epidemiological tool, but to assess the patient's perception of their recent respiratory problems.

Part 2 (Sections 9-17) addresses the patient's current state (i.e. how they are these days).

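### The Kaplan-Meier analysis of time to first exacerbation has no stated rule for death; if deaths are censored, it can slightly overstate the 12-month risk, and a cumulative incidence curve would avoid this.

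*Protocol*

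**What the plan says.** Protocol 8.7, secondary objective #2, lists three summaries: the proportion of patients with at least one exacerbation, the median number of episodes per patient, and a time-to-event display: "Finally time to first exacerbation will be analyzed by Kaplan-Meier curves". The synopsis repeats this. Neither place defines the event, the censoring rule or the treatment of death, and neither names a competing-risk method.

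For the proportion, the protocol does give a rule: "Patients who drop-out without having exacerbations before the end of the study, will be considered in the denominator of the proportion of interest".

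SAP section 3 (Computed Variables) closes the window for counting exacerbations, in patients who did not complete the study, at the "Date of drop out or death", without separating the two. It opens the window at IPF diagnosis, whereas the protocol speaks of 12 months of follow-up.

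On mortality, Protocol 6 gives an "estimated median survival time of 2 to 5 years following diagnosis", and Protocol 8.5 explains its 20 to 40% drop-out as follows: "Drop-out rate was hypothesized by considering mortality rate in IPF patients and natural drop-out from studies".

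No Kaplan-Meier output appears in the public SAP section on objective #2. Table numbers there skip from 24 to 26 and text was removed, so nothing is inferred from its absence.

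**The concern.** A patient who dies without an exacerbation can never have one. Kaplan-Meier knows only two outcomes, event or censored. If death is counted as an event, the curve shows exacerbation-free survival, which is a different quantity. If death is censored, the patient's remaining risk is in effect passed to the survivors. One minus Kaplan-Meier (1-KM) is then at least as large as the true cumulative incidence, and larger whenever someone dies exacerbation-free.

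Objective #2 is purely descriptive: how often these patients have exacerbations within 12 months. A risk in the hypothetical absence of death does not answer that. Sampling error is shown by a confidence interval; this bias is not, and it does not shrink as the sample grows.

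**Working it through.** **The plan's own figures.** The documents give no number for the Kaplan-Meier analysis. The study-size figures reproduce: 200 × (1 − 0.40) = 120 and 200 × (1 − 0.20) = 160 evaluable patients. For clubbing at n=120, 0.43 ± 1.96 × √(0.43 × 0.57 / 120) gives 34.1% to 51.9%, as printed in Table 1. The same formula serves as the precision yardstick below.

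**Inputs.** All come from Protocol 6. Median survival is 2 to 5 years; 5-year survival is 20 to 40%. On exacerbations: "Their yearly incidence is between 10 and 15% of all patients". Mortality of exacerbations is 78 to 96%.

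**Assumptions not in the documents.** Hazards are constant, deaths after an exacerbation fall within the year, and drop-out for reasons other than death is non-informative.

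**Step 1: one-year mortality.** 1 − 0.5^(1/5) = 12.9% and 1 − 0.5^(1/2) = 29.3%. From 5-year survival, 1 − 0.40^(1/5) = 16.7% and 1 − 0.20^(1/5) = 27.5%, inside the same range.

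**Step 2: upper bound, every death competing.** Let λ1 be the hazard of first exacerbation and λ2 that of death. Then 1-KM = 1 − exp(−λ1), and the cumulative incidence is CIF = λ1/(λ1+λ2) × (1 − exp(−(λ1+λ2))).

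- Reading 10% or 15% as 1-KM, the CIF is 8.48 to 9.35% or 12.74 to 14.03%. The excess is 0.65 to 2.26 points, or 7 to 18% in relative terms.
- Reading 10% or 15% as the CIF, which fits a percentage of all patients better, 1-KM is 10.70 to 11.79% or 16.03 to 17.65%. The excess is 0.70 to 2.65 points.

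**Step 3: only deaths before a first exacerbation compete.** With c the incidence, f the mortality of exacerbations and d the one-year mortality, competing deaths are c2 = d − f × c. Then λ1+λ2 = −ln(1 − c − c2), λ1 = (λ1+λ2) × c/(c+c2), and 1-KM = 1 − exp(−λ1).

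| Incidence c | Fatality f | Mortality d | Competing deaths c2 | 1-KM | Excess (points) |
|---|---|---|---|---|---|
| 10% | 78% | 12.9% | 5.1% | 10.28% | 0.28 |
| 10% | 78% | 29.3% | 21.5% | 11.32% | 1.32 |
| 10% | 96% | 12.9% | 3.3% | 10.18% | 0.18 |
| 10% | 96% | 29.3% | 19.7% | 11.19% | 1.19 |
| 15% | 78% | 12.9% | 1.2% | 15.10% | 0.10 |
| 15% | 78% | 29.3% | 17.6% | 16.60% | 1.60 |
| 15% | 96% | 12.9% | none left (−1.5%) | 15.00% | 0 |
| 15% | 96% | 29.3% | 14.9% | 16.32% | 1.32 |

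The mortalities derived from 5-year survival give 0.19 to 1.42 points, within this range.

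**Step 4: yardstick.** 1.96 × √(p(1−p)/n) for p = 10% and 15% is 4.16 and 4.95 points at n=200, and 5.37 and 6.39 points at n=120.

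**Step 5: the crude proportion.** As an illustration, read 15% as 1-KM (λ1 = −ln 0.85 = 0.1625), take a 5-year median with every death competing, and 40% total drop-out including deaths (combined hazard −ln 0.60 = 0.5108). The crude proportion is 0.1625/0.6733 × (1 − exp(−0.6733)) = 11.8%. The CIF is 14.0% and 1-KM is 15.0%. The two planned measures fall on opposite sides of the target.

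**The case against.** The strongest reply is that the curve is a supplement. The first-listed measure for objective #2 is the crude proportion, which keeps patients who die without an exacerbation in the denominator as non-events, and Protocol 8.7 also promises incidence rates for events. No test or treatment comparison depends on the curve. All of this stands and limits the importance of the point. It does not remove it: the crude proportion treats patients lost alive as event-free, so it cannot stand in for the curve.

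A second reply is that censoring at death is inferred. That also stands. The SAP rule that ends the window at drop-out or death was written for counting exacerbations, and the protocol does not say that 1-KM will be reported as the risk.

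A reader might go further and infer that the curve certainly overstates the risk, by 7 to 18% in relative terms, because one-year mortality is high. The documents do not support that. They state no one-year mortality; 13 to 29% is derived under a constant hazard and may not carry over to newly diagnosed patients selected for possible follow-up. The 7 to 18% treats every death as competing, although the protocol's 78 to 96% mortality of exacerbations means that many deaths follow the event. They do not all follow it in every scenario: with 2-year median survival, 10% incidence and 78% fatality, 21.5 of 29.3 deaths per 100 patients still compete.

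**Conclusion.** The point holds in a modest form. The plan leaves the handling of death open, and under the usual convention 1-KM can overstate the 12-month risk of exacerbation. On the protocol's own figures the excess is about 0 to 1.6 points, with a ceiling of about 2.7 points if every death competed. Both are below the sampling error at n=200. The range rests on constant hazards, on fatal exacerbations causing death within the year, and on deaths being censored. This is a cheap improvement to a secondary descriptive output. It does not invalidate objective #2.

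**What to change.** In Protocol 8.7 #2 and the SAP section on secondary objective #2, replace the Kaplan-Meier curve by the Aalen-Johansen cumulative incidence of first exacerbation. Treat death without exacerbation as the competing event and censor patients lost alive. Report the month-12 value with its 95% CI, and show death without exacerbation as a second curve.

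State the time origin. The protocol's 12 months of follow-up run from enrolment, while the SAP counts exacerbations since IPF diagnosis; the two must be reconciled before any curve is drawn.

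No new data are needed. Form F19 already holds the drop-out or death dates (SC_4, SC_5) and the cause of drop-out (SC_2), exacerbation onset dates are recorded, and survival status is scheduled at every follow-up visit. The SAP should say which F19 entries identify a death. The cost is SAP wording, slightly more programming, and a curve that may read slightly lower than Kaplan-Meier.

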8. RESEARCH METHODS

8.1 STUDY DESIGN

This is an observational, multicenter prospective cohort study based on newly collected data, involving 20 Italian Pulmonary Centers highly experienced in the disease management of IPF.

The enrolment period will last 18 months. During this period, about 200 consecutive patients will be included in agreement with the inclusion/exclusion criteria. Patients will be followed up for 1 year, with 3 intermediate evaluations after 3 (+/-1), 6 (+/-1) and 9 (+/-1) months from baseline (such visits are referred as being the current clinical practice in Italy for IPF patients management).

No treatment will be administered to the patients on the protocol basis, since this is an observational study and the assessment and treatment of the enrolled patients is based only on the investigators' clinical routine practice.

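### Scaling each patient's cost to one year and then averaging is expected to overstate mean annual cost of illness, because early deaths are scaled up although death ends cost

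*Protocol*

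**What the plan says.** Protocol 8.7 (secondary objective #4, repeated in the synopsis) costs the resources used from diagnosis to the end of follow-up. It then provides a monthly or yearly cost, "taking into account patients according to duration of observation and parametrizing each patient to the 1-year observation period". Cost of illness is summarised by mean, SD, median, minimum and maximum, and "Non-parametric bootstrap method will be applied to COI data for calculating 95% confidence intervals".

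On the time base, Protocol 8.1 states that "Patients will be followed up for 1 year", counted from baseline. The cost window opens earlier: "Health care resources consumed during a three-month span of time between date of diagnosis and inclusion in the study will be retrospectively collected". The protocol does not say whether these pre-enrolment months also enter the denominator of the annualisation.

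On incomplete follow-up, Protocol 8.5 assumes 20-40% drop-out and explains that "Drop-out rate was hypothesized by considering mortality rate in IPF patients and natural drop-out from studies".

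No text available for review weights patients by time observed, separates death from loss to follow-up for costs, or sets a minimum observation time. SAP 4.8 covers this objective with resource-use tables. The costing rule is visible only in the protocol.

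**The concern.** Death ends cost. A patient who dies within 12 months has a complete cost history, and what was spent is the whole 12-month cost. Only a patient lost to follow-up has costs that are unseen. The stated rule treats the two alike and scales both up.

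That matters when short observation and high cost go together, and the protocol's background (Section 6) says they will. Exacerbations strike 10-15% of patients a year, carry 78-96% mortality and are thought to account for at least half of hospitalisations. The patients with the largest scaling factors are then those whose last weeks were most expensive. One-off costs around diagnosis are scaled by the same factor.

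Mean annual cost is the figure a payer would take from objective #4. If it is too high, the SD is inflated with it. The bootstrap resamples the same scaled values, so it describes sampling error around the wrong quantity and does not remove the bias.

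**Working it through.** **Figures the protocol supports.** Drop-out: 200 × (1 − 0.40) = 120 and 200 × (1 − 0.20) = 160, which reproduces the stated range of evaluable patients. Deaths from exacerbation: 0.10 × 0.78 = 7.8% to 0.15 × 0.96 = 14.4% a year, about 16 to 29 of 200, if those deaths fall within the year. The documents give no costs or death times, so every cost below is assumed.

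**Formulas.** Let b be background cost per year, L the cost of a terminal episode, D = 1 if the patient dies under observation, and t the years observed. One patient's annualised cost is (b·t + L·D)/t = b + L·D/t.

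- Mean of annualised costs: b + L·E[D/t]
- Total cost / total person-time: b + L·P(D)/E[t]
- Cost accrued in 12 months, without loss to follow-up: b·E[min(T,1)] + L·P(T ≤ 1), with T the time to death

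The first exceeds the second by L × (E[D/t] − P(D)/E[t]). This is driven by 1/t among those who die.

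**Hand example.** Assume b = 12,000 euro, L = 10,000 euro, and 14.4% dying at 3 months.

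- Annualised mean: 0.856 × 12,000 + 0.144 × (3,000 + 10,000) × 4 = 10,272 + 7,488 = 17,760
- Accrued in 12 months: 10,272 + 0.144 × 13,000 = 12,144
- Per person-year: 12,144 / (0.856 + 0.144 × 0.25) = 12,144 / 0.892 = 13,614

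The annualised mean is 1.30 times the person-time figure and 1.46 times the accrued cost.

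Now add three months before enrolment, in cost and time, for everyone. Deaths have 6,000 + 10,000 = 16,000 over half a year, so 32,000 annualised.

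- Annualised mean: 10,272 + 0.144 × 32,000 = 14,880
- Per person-year: (0.856 × 15,000 + 0.144 × 16,000) / (0.856 × 1.25 + 0.144 × 0.5) = 15,144 / 1.142 = 13,261

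The excess falls to 12%.

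**Range.** Assume b = 8,000 euro, L = 4,000-12,000 euro, death hazard 0.12-0.25 a year and loss hazard 0.10-0.25 a year. Patients observed for under one month after enrolment are left out. The hazards give 1 − exp(−0.22) = 20% to 1 − exp(−0.50) = 39% incomplete, matching Protocol 8.5.

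For hazards 0.2 and 0.1, L = 8,000 and time from enrolment: P(D) = 0.1603, E[t] = 0.8848 and E[D/t] = 0.4575. The annualised mean is 8,000 + 8,000 × 0.4575 = 11,660. The person-time figure is 8,000 + 8,000 × 0.1603/0.8848 = 9,449. The excess is 23%.

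Across the corners of the grid:

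| Start of the time denominator | Excess over total cost / total person-time |
|---|---|
| Enrolment | about 8-38% |
| Diagnosis, uniform 0-3 months before enrolment | about 4-23% |
| Diagnosis, a full 3 months for everyone | about 3-14% |

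The low end is death hazard 0.12, loss 0.25, L = 4,000. The high end is death hazard 0.25, loss 0.10, L = 12,000.

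**No minimum time, clock from enrolment.** With a constant death hazard the integral of 1/t diverges at zero, so the expectation is infinite. Simulated excess was 35%, 41%, 110% and 67% at rising run sizes and did not settle.

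**Check of the remedy.** In simulation, an inverse-probability-of-censoring weighted mean, with death as a complete observation, returned 12,546 against a true 12-month cost of 12,544.

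**The case against.** The equal-weight mean of scaled values is inferred. The protocol's wording is loose, and taking duration of observation into account could describe a time-weighted rate, which would avoid this inflation. But "parametrizing each patient to the 1-year observation period" points to scaling one patient at a time, and that is the plain reading. If a rate was intended, one sentence settles it.

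The direction is not a mathematical certainty. If the cost rate is constant and unrelated to survival, the annualised mean equals the person-time figure. If early deaths have half the cost rate and no terminal episode, a simulation gave 11,129 against 11,535, so the annualised mean was lower. It was still above the accrued 12-month cost of 10,692. A reader might infer that overstatement is proven. The documents make costly deaths likely but do not quantify them.

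A reader might also infer that an admission before death at two months counts six times. That holds only if the clock starts at enrolment (12/2 = 6). With three pre-enrolment months in the denominator the factor is 12/5 = 2.4. Nor can a fixed excess be quoted for the case with no minimum time, since that mean does not converge.

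Finally, the protocol also mentions costs at diagnosis, so separate reporting of that phase is partly foreseen. The median and maximum would reveal extreme scaled values. The objective is descriptive, with no test attached. These points limit the consequences, but the median cannot give a total burden for the health service.

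**Conclusion.** The point holds on the plain reading of Protocol 8.7. Annualising each patient and averaging is expected to overstate mean annual cost and its SD, and the bootstrap interval is then placed around the wrong quantity. The size cannot be fixed from the documents. Under the assumed costs and hazards, with at least one month observed, the excess over total cost / total person-time is roughly 3% to 38%, depending mostly on where the clock starts and how costly the terminal episode is. Without a minimum observation time and with time from enrolment, the mean is unstable. The upward direction against the person-time figure rests on cost being concentrated near death, which Section 6 makes probable but not certain. This should be corrected before the cost analysis is run. It does not touch the primary objective.

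**What to change.** In Protocol 8.7, and wherever the SAP specifies the costing:

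- State the estimand: mean cost accrued over 12 months, or cost per person-year. State whether time is counted from diagnosis or from enrolment.
- Do not scale up patients who die. Treat death within 12 months as a complete cost history.
- Estimate mean 12-month cost with a censoring-adjusted estimator, for example inverse-probability-of-censoring weighting in which only loss to follow-up counts as censoring. At minimum, report total cost / total person-time, labelled as a cost per person-year.
- Report the diagnosis-to-enrolment cost separately, without annualising it.
- Bootstrap the chosen estimator by resampling patients and recomputing it in each resample.

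No new data are needed. The cost is a few sentences of text, modest extra programming and a headline figure that will probably be lower.
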